9.3. Efficacy Analysis

All efficacy analyses will be performed on the Full Analysis Set unless otherwise specified. Some efficacy analyses will also be performed on the Safety Analysis Set.

All analyses will be performed by using SAS[®] Version 9.1.3 or higher.

All secondary endpoints based on radiological assessments of tumor burden (ie, PFS, OR, DR, DC) will be derived using the local radiologist's/investigator's assessment. Radiographic images and clinical information collected on study will also be reviewed by a BICR to verify investigator reported tumor assessments. This information will be used for supportive analyses, except for PFS whose assessment by BICR is a primary endpoint.

Sensitivity analyses will be described in the SAP.

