6.2.2. Efficacy endpoints

The following analyses will be based on the FAS by treatment arm unless otherwise specified. Assessment of response will be made using RECIST v1.1.

Analyses for tumor-related endpoints will be performed based on BICR assessment and based on Investigator assessment. PFS by investigator assessment will be analyzed as a secondary endpoint using the same methodology that is described in Section 6.1.2.1 now referring to PD by investigator assessment instead of PD by BICR assessment. RCIs will not be constructed for the hazard ratio of PFS by investigator assessment.

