The EDR represents the positive predictive value of investigator assessment and quantifies the frequency with which the investigator declares PFS event earlier than BICR within each treatment arm as a proportion of the total number of investigator assessed events.

The LDR quantifies the frequency with which the investigator declares PFS event later than BICR as a proportion of the total number of discrepancies within the treatment arm.

Discordance metrics are calculated for each treatment arm and, for each metric, the difference in discordance between the experimental and control arms is used to evaluate potential bias. If the discordance is similar across the treatment arms then this suggests the absence of evaluation bias favoring a particular treatment arm. A negative differential discordance for EDR and/or a positive differential discordance for LDR may be indicative of investigator evaluation bias in favor of the experimental arm (Amit et al, 2011).

Exploratory analyses to investigate the impact of potential prognostic or effect modifying (predictive) factors

The same methodology described in Section 6.2.2.1 for OS will be used for PFS based on BICR assessment.

090177e19142bcd4\Approved\Approved On: 09-Jul-2019 05:44 (GMT)

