The stratified odds ratio in terms of OR will also be estimated along with its 95% CI to compare study treatments. The odds ratio is defined as the odds of OR with experimental treatment divided by the odds of OR with control treatment. The Breslow-Day test will be used to check the homogeneity of the odds ratio across the randomization strata. It tests the null hypothesis that odds ratios in all strata are equal against the alternative hypothesis that at least in one stratum the odds ratio is different.

In case the null hypothesis of homogeneity of odds ratios across strata is not rejected at the 2-sided alpha level of 0.05, the common odds ratio will be determined using the Mantel-Haenszel estimate (by the FREQ procedure using CMH option in SAS); if the null hypothesis of homogeneity of odds ratio across all strata is rejected, the odds ratio per stratum will be calculated with the corresponding exact CI.

BICR vs Investigator Assessment:

Table 12 outlines the possible BOR outcomes by investigator and BICR.

Table 12. Possible BOR Outcomes for Investigator vs BICR

BOR		BICR Assessment					
		CR	PR	SD	Non-CR/ non-PD	PD	NE
Investigator Assessment	CR	n ₁₁	n ₁₂	n ₁₃	n ₁₄	n ₁₅	n ₁₆
	PR	n ₂₁	n ₂₂	n ₂₃	n ₂₄	n ₂₅	n ₂₆
	SD	n ₃₁	n ₃₂	n ₃₃	n ₃₄	n ₃₅	n ₃₆
	Non-CR/ non-PD	n ₄₁	n ₄₂	n ₄₃	n ₄₄	n ₄₅	n ₄₆
	PD	n ₅₁	n ₅₂	n ₅₃	n ₅₄	n ₅₅	n ₅₆
	NE	n ₆₁	n ₆₂	n ₆₃	n ₆₄	n ₆₅	n ₆₆

$\sum_{i=1}^6(n_{ii})$ is the number of agreements on BOR between BICR and Investigator

$\sum_{i,j=1}^6(n_{ij})$ for $i \neq j$ is the number of disagreements on BOR between BICR and Investigator

$N = \sum_{i,j=1}^6(n_{ij})$

The following measures of concordance will be calculated for each treatment arm:

- Concordance rate for BOR = $\sum_{i=1}^6(n_{ii}) / N$
- Concordance rate for response = $[\sum_{i,j=1}^2(n_{ij}) + \sum_{i,j=3}^6(n_{ij})] / N$

Concordance rates are calculated for each treatment arm and, for each metric, the difference in concordance between the experimental and control arms are used to evaluate potential bias. If the concordance is similar across the treatment arms then this suggests the absence of evaluation bias favoring a particular treatment arm.

Tumor Shrinkage from baseline:

Tumor shrinkage will be summarized as the percent change from baseline in target lesions (sum of longest diameter for non-nodal lesion and short axis for nodal lesion) per time point. It will be derived as:

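### Similar investigator–BICR concordance across arms cannot support the SAP's statement that response evaluation bias favouring an arm is absent, because both concordance rates ignore the direction of disagreement

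*SAP*

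**What the plan says.** SAP 6.2.2.3, in the part comparing BICR with the investigator, cross-classifies best overall response by the two readers (Table 12) and derives two measures per arm. The BOR concordance rate is the diagonal of the six-by-six table divided by N. The "Concordance rate for response" adds patients whom both readers call responders to patients whom both call non-responders, divided by N. For each measure, "the difference in concordance between the experimental and control arms are used to evaluate potential bias", and the inference offered is "If the concordance is similar across the treatment arms then this suggests the absence of evaluation bias favoring a particular treatment arm". No signed measure is defined for response, and no threshold or test says what counts as similar.

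For PFS, SAP 6.2.2.2 uses early and late discrepancy rates (EDR and LDR) with a signed rule for detecting a lean towards avelumab: "A negative differential discordance for EDR and/or a positive differential discordance for LDR may be indicative of investigator evaluation bias in favor of the experimental".

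The trial is open-label. Protocol 9.3 says that the secondary tumor endpoints "will be derived using the local radiologist's/investigator's assessment", with BICR supportive except for PFS. Protocol 9.3.2 and SAP 6.2.2 report both readings: "Analyses for tumor-related endpoints will be performed based on BICR assessment and based on Investigator assessment".

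**The concern.** Bias towards an arm means that, in that arm, investigators call response where BICR does not more often than the reverse, relative to the other arm. The two off-diagonal groups that carry this information are merged into one disagreement total. The SAP therefore draws a directional inference from a measure without direction, although its own PFS check has direction.

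At stake is the credibility of investigator-assessed objective response in an open-label trial. SAP 6.2.2.3 tests objective response at one-sided 0.025, and the concordance comparison is the only bias check that the SAP states for response.

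**Working it through.** The documents give no expected concordance or disagreement rate, so there is no planned figure to reproduce. The arm size follows from the plan: about 550 patients randomized 1:1:1, and 550/3 ≈ 183. All cell values below are assumptions.

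**1. Symmetry.** Let *u* be the share with investigator-only response (upgrades) and *d* the share with BICR-only response (downgrades).

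- Response concordance = 1 − (*u* + *d*).
- Investigator ORR − BICR ORR = *u* − *d*.

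The first depends only on the sum, so swapping the readers leaves it unchanged. The diagonal of Table 12 is likewise unchanged when the table is transposed. Neither planned rate can show which way investigators lean.

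**2. Same net shift, different mechanisms.** BICR ORR is 12% in both arms. Control has *u* = *d* = 3.5%, so its concordance is 1 − 0.07 = 93%.

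- Upgrades replace downgrades in the avelumab arm: *u* = 7%, *d* = 0. Concordance = 1 − 0.07 = 93%; *u* − *d* = +7 points.
- Upgrades are added to unchanged downgrades: *u* = 10.5%, *d* = 3.5%. Concordance = 1 − 0.14 = 86%; *u* − *d* = +7 points.

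Each case was simulated with 20,000 multinomial trials. The 5-point band and the CI for the concordance difference are yardsticks chosen here; the SAP sets neither. The variance of *u* − *d* in an arm is [(*u* + *d*) − (*u* − *d*)²]/n.

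| Avelumab *u*/*d* (control 3.5/3.5) | Concordance, avelumab vs control | False ORR difference | Concordance within 5 points | CI for concordance difference excludes 0 | CI for signed difference excludes 0 |
|---|---|---|---|---|---|
| 3.5/3.5 | 93% vs 93% | 0 | 95% | 5% | 5% |
| 7/0 | 93% vs 93% | +7 | 95% | 5% | 75% |
| 10.5/3.5 | 86% vs 93% | +7 | 28% | about 60% | about 57% |

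An intermediate mechanism is a more lenient investigator threshold on a bivariate-normal scale, calibrated to 7% disagreement without bias. For the same +7 points it gives concordance of 89.9% vs 93%, within 5 points in about 76% of trials.

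**3. Whole patients.** Take 27 BICR responders per arm and let every disagreement be PR against SD, so that both concordance rates coincide.

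- Control: 20 agreed responders, 7 upgrades, 7 downgrades. Concordance = (183 − 14)/183 = 92.3%; investigator ORR = 27/183 = 14.8%.
- Avelumab: 27 agreed responders, 14 upgrades, 0 downgrades. Concordance = 169/183 = 92.3%; investigator ORR = 41/183 = 22.4%.
- BICR ORR is 14.8% in both arms. The investigator odds ratio is (41/142)/(27/156) = 1.67, unstratified one-sided p = 0.030.
- With 6, 10 or 14 discordant patients per arm, all upward in avelumab and balanced in control, the hidden shift is 6/183 = 3.3, 10/183 = 5.5 or 14/183 = 7.7 points.
- If the 7 downgrades had stayed and 7 upgrades were added, concordance would be 162/183 = 88.5%.

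**4. No bias, but unequal true response.** Take BICR as truth, ORR 20% vs 10%, and the same investigator sensitivity (75%) and specificity (98%) in both arms.

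- Concordance: 0.20×0.75 + 0.80×0.98 = 93.4%; 0.10×0.75 + 0.90×0.98 = 95.7%. Difference −2.3 points.
- Investigator minus BICR ORR: (0.150 + 0.016) − 0.20 = −3.4 points; (0.075 + 0.018) − 0.10 = −0.7 points. Difference −2.7 points.

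Unequal concordance therefore does not show bias either, and the signed difference also drifts.

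**The case against.** Four objections deserve weight.

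- **The check has some sensitivity.** Full masking requires upgrades to be offset by fewer downgrades, or the control arm to have equal but balanced disagreement. Added upgrades lower concordance and would usually be visible. This stands. A reader might infer that the SAP's check returns a reassuring answer as often with bias as without it; the third row of the table shows that this is not generally true.
- **The direction is already recoverable.** ORR by arm is planned for both readers, and Table 12 contains every cell. This stands in part: the subtraction is easy, but the SAP does not link it to the bias assessment and gives it no interval.
- **The signed measure is imperfect.** In step 4 it drifts slightly more than concordance, and in the direction that would mask bias towards avelumab when avelumab truly has the higher response rate. This stands and limits how it may be read.
- **The consequences are narrow.** SAP 5.1.1 allocates alpha to OS and BICR-assessed PFS, with gatekeeping for time to deterioration. The subset analyses of response (SAP 6.4) and the interim ORR summary (Protocol 9.6.3) use BICR, and no decision rule depends on concordance. This also stands.

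None of these rescues the inference sentence, because agreement alone cannot speak to which arm is favoured.

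**Conclusion.** The concern holds in a limited form. Similar concordance does not support absence of bias towards an arm. With 7% disagreement and balanced disagreement in control, concordance can be identical while investigator ORR is inflated by up to 7 points against a BICR difference of 0. That size rests on the assumed disagreement rate and scales with it.

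Three stronger readings are not supported:

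- The check is not blind to every biased pattern.
- The SAP does not conclude that bias is absent; its wording is that similarity *suggests* absence.
- The primary results are not at risk, since OS needs no tumor reading and primary PFS is read by BICR.

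This is a worthwhile correction to a diagnostic for secondary endpoints.

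**What to change.** In SAP 6.2.2.3:

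- Report by arm the proportions with investigator-only and BICR-only response, both sums of Table 12 cells.
- Report the arm difference in (investigator ORR − BICR ORR) with a 95% CI from the paired-proportion variance in each arm.
- Keep both concordance rates as descriptive.
- Delete the sentence that similar concordance suggests absence of bias, or reword it to say that concordance measures agreement and not direction. This brings response into line with the directional approach to PFS in SAP 6.2.2.2.

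The cost is SAP wording and one extra table line; no new data, alpha or design change is needed. The SAP should state the downside. The signed difference is imprecise with few responders: in the 7/0 case its standard error is √[(0.0651 + 0.07)/183] ≈ 2.7 points, a 95% CI half-width of about 5.3 points. It also drifts when true response rates differ, by about −2.7 points in step 4 of the working. It should be read with its CI and beside the two discordance rates, not as a stand-alone test of bias.

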6.2.2.4. Disease control

Disease Control (DC) is defined as BOR of CR, PR, non-CR/non-PD or SD. Both CR and PR must be confirmed by repeat assessments performed no less than 4 weeks after the criteria for response are first met. DC rate (DCR) is the proportion of patients with DC.

DCR will be summarized by frequency counts and percentages.

6.2.2.5. Duration of response

Duration of Response (DR) is defined, for patients with OR, as the time from the first documentation of objective response (CR or PR) to the date of first documentation of PD or death due to any cause. If a patient has not had an event (PD or death), DR is censored at the date of last adequate tumor assessment. The censoring rules for DR are as described for PFS in Table 9.

$$\text{DR (months)} = [\text{date of event or censoring} - \text{first date of OR} + 1] / 30.4375$$

Kaplan-Meier estimates (product-limit estimates) will be presented by treatment arm together with a summary of associated statistics including the median DR time with 2-sided 95% CIs. In particular, the DR rate at 3, 6, 9, 12 and 15 months will be estimated with corresponding 2-sided 95% CIs. The CIs for the median will be calculated according to Brookmeyer and Crowley (1982) and the CIs for the survival function estimates at the time points defined above will be derived using the log-log transformation according to Kalbfleisch and Prentice (2011) (confype=loglog default option in SAS Proc LIFETEST) with back transformation to a CI on the untransformed scale. The estimate of the standard error will be computed using Greenwood's formula.

DR will be displayed graphically and analyzed using Kaplan-Meier methodology. If the number of patients with OR is small, the Kaplan-Meier method may not provide reliable estimates. In this case, only descriptive statistics or listings will be provided.

6.2.2.6. Time to response

Time to response (TTR) is defined, for patients with OR, as the time from the date of randomization to the first documentation of objective response (CR or PR) which is subsequently confirmed.

$$\text{TTR (in months)} = [\text{first date of OR} - \text{date of randomization} + 1] / 30.4375$$

TTR will be summarized using simple descriptive statistics (mean, SD, median, min, max, Q1, Q3).

6.2.3. Pharmacokinetic endpoints

The following pharmacokinetic analyses will be based on the PK analyses set by treatment arm.

C_{trough} and C_{max} for avelumab and doxorubicin will be summarized descriptively (n, mean, SD, CV, median, minimum, maximum, geometric mean, its associated CV, and 95% confidence interval) by treatment arm, cycle, and day. Other standard parameters will be calculated including, but not limited to AUC_{24} , T_{max} , AUC_{last} , T_{last} , $AUC_{\text{sd},\tau}$, $AUC_{\text{ss},\tau}$, $t_{1/2}$, CL , Vd_z , $C_{\text{ss,av}}$ as data permit.

Dose normalized parameters (eg, $CDN - C_{\text{max}}$, $DN - AUC$) will be reported as appropriate. The trough concentrations for avelumab and doxorubicin (for each dose as needed) will be plotted using a box whisker plot by cycle and day in order to assess the attainment of steady state.

Pharmacokinetic parameters for avelumab and doxorubicin will be taken from observed values or derived from plasma concentration-time data as described in Section 3.2.4.

Presentation of pharmacokinetic data will include:

- Descriptive statistics (n, mean, SD, %CV, median, minimum, maximum) of plasma concentrations will be presented in tabular form by treatment arm, dose level (for doxorubicin as needed), cycle, day and nominal time. Additionally similar descriptive statistics will also be generated for dose-normalized avelumab and doxorubicin pharmacokinetic parameters.
- Linear-linear and log-linear plots of mean and median plasma concentrations by nominal time for avelumab and doxorubicin will be presented for PK sampling days by treatment arm, cycle, and study day. Similar plots will be presented for each individual patient concentrations. Patients who have undergone inpatient dose reduction or escalation will be excluded from the median plasma concentration-time plots.
- Pharmacokinetic parameters for avelumab and doxorubicin will be listed and summarized by treatment arm/dose level (for doxorubicin as needed), cycle and study day using descriptive statistics (n, mean, SD, %CV, median, minimum, maximum, geometric mean and its associated %CV, and 95% confidence interval). For T_{max} , the range (min, max) will also be provided. PK parameters with zero values will be excluded from the calculation of geometric means and their associated %CV. If an inpatient dose

escalation or reduction occurs, dose-dependent PK parameters (AUC and C_{max}) for that patient may be dose-normalized when it is known that the drug exhibits linear PK within the dose range and other PK parameters will be reported as estimated; or may only be included in descriptive statistics and summary plots up to the time of the dose change. In addition, dose-normalized C_{max} and AUC parameters will be summarized (as described above) using data pooled across treatment arms in which different avelumab and doxorubicin doses were administered.

- Box plots for AUC and C_{max} for avelumab and doxorubicin will be generated. Individual data points, the geometric mean and the median of the parameter in each treatment will be overlaid on the box plots. If a treatment arm has limited evaluable PK data (n<4), matchstick plots showing changes in AUC and C_{max} for each drug in individual patients will then be generated. The geometric mean of the parameter in each treatment will be overlaid in the plots.
- C_{trough} and C_{max} for avelumab will be plotted for each treatment arm using a box-whisker plot by cycle and day within cycle in order to assess the attainment of steady-state.

Assessment of drug-drug interaction

Effect of Avelumab on Doxorubicin (PLD Samples) Pharmacokinetics

The effect of avelumab dosing on doxorubicin PK will be evaluated based on overall assessment of the geometric mean ratios and associated 90% CI for C_{max}, AUC_{inf}, and AUC_τ of PLD on Day 1 of Cycle 2 in Arm B (avelumab plus PLD) compared to those on Day 1 of Cycle 2 of Arm C.

Effect of PLD on Avelumab Pharmacokinetics

The effect of PLD dosing on avelumab PK will be evaluated based on the overall assessment of the geometric mean ratios of C_{max} and C_{trough} of Arm B on Day 1 of Cycle 2 compared to those on Day 1 of Cycle 2 of Arm A.

6.2.4. Population pharmacokinetic endpoints

Pharmacokinetic and pharmacodynamic data from this study may be analyzed using modeling approaches and may also be pooled with data from other studies to investigate any association between avelumab exposure and biomarkers or significant safety/efficacy endpoints. The results of these analyses, if performed, may be reported separately.

6.2.5. Biomarker endpoints

Secondary endpoints in the study are candidate predictive biomarkers in tumor tissue including, but not limited to, PD-L1 expression and tumor infiltrating CD8+ T lymphocytes as assessed by immunohistochemistry (IHC).

Biomarker data will be analyzed based on the biomarker analysis sets as defined in Section 4.3.3, by treatment arm.

For PD-L1 expression, patients will be classified as positive and negative according to scoring algorithms and cut-offs established from internal or external sources. Patients whose status cannot be determined are not considered to have screening biomarker assessment per the biomarker analysis set definition, and therefore will be excluded.

For CD8+, if at the time of reporting an internal or external standard becomes available, the above mentioned approach for PD-L1 will be used. Otherwise, data will be categorized using quartiles to define CD8+ subgroups.

The following analyses will be performed for each biomarker secondary endpoint.

Biomarker subgroups as defined above will be used to perform subgroup analyses for efficacy endpoints (BOR and PFS by BICR assessment, OS) using the methodology outlined in Section 6.4. In addition, for PFS by BICR assessment and OS, the hazard ratio for the biomarker subgroup level comparisons and the unadjusted 95% CIs for the hazard ratio will be reported for each treatment arm.

CCI
CA-125 levels. CCI

6.2.6. Endpoints for immunogenicity data of avelumab

All analyses described below are performed by treatment arm containing avelumab (Arm A and Arm B), and for the avelumab-containing treatment arms combined unless otherwise specified.

Blood samples for avelumab immunogenicity testing will be collected within 2 hours before the start of the avelumab infusion on Day 1 of Cycles 1 through 4. Thereafter, a sample will be collected on Day 1 prior to avelumab infusion in Cycles 5, 6, 9, 12, 15, 18, 21 24 and at the End of Treatment. An additional sample must be collected at 30 days after the last dose of avelumab.

Samples positive for ADA will be analyzed for titer and may be analyzed for nAb. As of the finalization of this SAP, the nAb assay is not yet available, therefore the analyses of nAb data described in the following sections will only be conducted contingent upon assay and data availability at the time of reporting.

Patients will be characterized into different ADA categories based on the criteria defined in [Table 13](#).

Table 13 Patients Characterized Based on Anti-Drug Antibody Results (ADA Status)

Category	Definition	Subjects at Risk (Denominator for Incidence)
ADA never-positive	No positive ADA results at any time point; ADA-negative patients (titer < cutpoint)	Number of patients with at least one valid ADA result at any time point
ADA ever-positive	At least one positive ADA result at any time point; ADA-positive patients (titer ≥ cutpoint)	Number of patients with at least one valid ADA result at any time point
Baseline ADA positive	A positive ADA result at baseline	Number of patients with valid baseline ADA result
Treatment-boosted ADA	A positive ADA result at baseline and the titer ≥ 8×baseline titer at least once after treatment with avelumab	Number of patients with valid baseline ADA results and at least one valid post-baseline ADA result
Treatment-induced ADA	Patient is ADA-negative at baseline and has at least one positive post-baseline ADA result; or if patient does not have a baseline sample, the patient has at least one positive past-baseline ADA result	Number of patients with at least one valid post-baseline ADA result and without positive baseline ADA result (including missing, NR)
Transient ADA response	If patients with treatment-induced ADA have (a single positive ADA result or duration between first and last positive result <16 weeks) and ADA result at the last assessment is not positive.	Number of patients with at least one valid post-baseline ADA result and without positive baseline ADA result (including missing, NR)
Persistent ADA response	If patients with treatment-induced ADA have duration between first and last positive ADA result ≥16 weeks or a positive ADA result at the last assessment	Number of patients with at least one valid post-baseline ADA result and without positive baseline ADA result (including missing, NR)

ADA: anti-drug antibody, NR = not reportable.

Patients will be characterized into different nAb categories based on the criteria in [Table 14](#). For nAb, treatment-boosted is not applicable since no titer result is available.

Table 14 Patients Characterized Based on Neutralizing Antibody Results (nAb Status)

Category	Definition	Subjects at Risk (Denominator for Incidence)
nAb never-positive	No positive nAb results at any time point	Number of patients with at least one valid ADA result at any time point
nAb ever-positive	At least one positive nAb result at any time point	Number of patients with at least one valid ADA result at any time point
Baseline nAb positive	A positive nAb result at baseline	Number of patients with valid baseline ADA result
Treatment-induced nAb	Patient is not nAb positive at baseline and has at least one positive post-baseline nAb result; or if patient does not have a baseline sample, the patient has at least one positive post-baseline ADA result	Number of patients with at least one valid post-baseline ADA result and without positive baseline nAb result (including missing, NR)
Transient nAb response	If patients with treatment-induced nAb have (a single positive nAb result or duration between first and last positive result <16 weeks) and nAb result at the last assessment is not positive.	Number of patients with at least one ADA valid post-baseline result and without positive baseline nAb result (including missing, NR)
Persistent nAb response	If patients with treatment-induced nAb have duration between first and last positive nAb result ≥16 weeks or a positive nAb result at the last assessment	Number of patients with at least one valid post-baseline ADA result and without positive baseline nAb result (including missing, NR)

ADA = antidrug antibody, nAb = neutralizing antibody, NR = no result.

The number and percentage of patients in each ADA and nAb category will be summarized.

